### **13.7 Subject Disposition and Protocol Deviations**

The number of subjects included in each of the study populations (ITT, PP, SP) will be summarized overall, by treatment group as randomized, and by study site. A listing sorted by treatment group and subject will be provided that will include the reasons for exclusion from any of the study populations. The number of subjects enrolled, excluded, discontinued, prematurely withdrawing from the study, lost to follow-up, evaluable, completed and the reasons for classification will be summarized and listed by treatment group for all subjects in the ITT population. Protocol deviations will also be summarized by treatment group and listed.

### **13.8 Demographic and Baseline Characteristics**

Subjects' demographic and baseline characteristics include but are not limited to (1) age; (2) gender; (3) race; (4) ethnicity; (5) medical history conditions; and (6) AF history and will be summarized overall and by treatment group. The descriptive statistics including number of subjects, mean, median, 25th and 75th percentiles, minimum, maximum and standard deviation will be presented for continuous variables. Frequency and percentage will be presented for ordinal and categorical variables. Fisher's exact tests will be used to examine the categorical, demographic, and baseline characteristics between two groups, and Kruskal-Wallis tests will be used for the continuous variables as appropriate.

### **13.9 Primary Statistical Analyses**

#### **13.9.1 Primary Effectiveness Analysis**

The primary effectiveness analysis will be a Kaplan-Meier (KM) analysis for all subjects in the ITT population and account for censored observations. The primary effectiveness analysis will be performed in the ITT population where the subjects will be attributed to the treatment group as randomized, regardless of treatment cross-over or post-randomization medical care. A log-rank test will be used to compare the hazard functions between the two groups at any observed event time. The median time to persistent AF/AT as well as the 95% confidence intervals will be reported by treatment group. The survival probability and rate of persistent AF/AT at 3 years follow-up as well as the 95% confidence intervals for both groups will be presented.

The effect size is defined as the negative log of the hazard ratio (hazard rate of the Test Group over hazard rate of the Control Group):  $\delta = -\log_e(\lambda_t/\lambda_c)$

This study is to test the following hypothesis using a one-sided test at alpha equal to 0.025:

H0:  $\delta \leq 0$

H1:  $\delta > 0$

Null hypothesis: the hazard rate in the Test Group is greater than or equal to the hazard rate in the Control Group at observed event times during the follow-up period

Alternative hypothesis: the hazard rate in the Test Group is less than the hazard rate in the Control group at observed event times during the follow-up period

At any interim monitoring calendar time  $l_j$ , we compute the Z statistic at information fraction  $t_j$  using the standardized logrank score statistic:

$$Z(t_j) = \frac{S(l_j)}{\sqrt{V(l_j)}}$$

where  $S(l_j)$  is the observed logrank score statistic at calendar time  $l_j$ , and  $V(l_j)$  is the variance of  $S(l_j)$ .

The Z test statistic will be compared with the stopping boundaries to determine whether this study will be stopped for effectiveness in each of the interim analyses. If the Z statistic crosses the stopping boundary, that is, Z is greater than the critical value at the interim look, then the study will be stopped for effectiveness. If the sample size exceeds the pre-planned sample size, then the CHW (Down-Weight) adaptive method will be used for statistical testing.

Conditional power will be calculated after the 1st interim look to assist the determination of whether the study will be stopped for futility.

### 13.9.2 Interim Analyses

An interim examination of the primary endpoint data will be performed at regular time intervals during the course of the trial to determine whether the study will be stopped for effectiveness or futility. The primary objective of this study is to determine whether early RF ablation treatment using the CARTO® 3, CARTO® XP or CARTO® RMT System and THERMOCOOL® Catheter Family in the PAF population delays progression of AF compared with AAD therapy (either rate or rhythm control) using current AF management guidelines. In addition, interim reporting will also involve a review of subject recruitment, compliance with the study protocol, status of data collection, safety endpoints and other factors that may affect the overall progress and integrity of the study. The results of the interim analyses and status reports will be reviewed by the Data Safety Monitoring Committee (DSMC).

The DSMC will review the accumulated data at 1 year following the study startg and then approximately every 6 months thereafter. Prior to each review, Biosense Webster will conduct statistical analyses and prepare an interim summary report. The progress of subject enrollment, the rates of compliance with therapy, the frequency of protocol violations and rates of safety endpoints will be reviewed. The number (status) of eCRFs completed, the number of outstanding data queries, the number of data queries completed, and the number of eCRFs reviewed through on-site monitoring will also be reviewed. Extracted data files and analysis programs for each interim report will be archived in the study files.

---

g Time-interval related statistical deliverables are subject to change depending on the evolution of the study (e.g. delay in start-up, enrolment delay, ...).

Interim effectiveness reports introduce well-recognized statistical problems related to the multiplicity of statistical tests performed on an accumulating set of data. To properly account for the repeated interim testing in this study, a group sequential method similar to that proposed by O'Brien and Fleming as a guide in interpreting interim analyses will be used. This procedure requires large critical values early in the study, but relaxes (i.e., decreases) the critical value as the trial progresses. Because of the conservatism early in the trial, the critical value at the final analysis is near the "nominal" critical value. Hence the sample size requirements with this group sequential procedure remain essentially the same as the conventional fixed sample size estimate. The actual method for the interim reporting that will be employed in this study is the "alpha-spending function" approach to group sequential testing developed by Lan and DeMets. The Lan-DeMets approach is flexible to accommodate unequal sized groups with the number of interim looks unspecified in advance. It only requires specification of the rate at which the Type I error (which in this trial will be  $\alpha=0.025$  for the primary endpoint) will be "spent". This procedure allows "spending" a portion of  $\alpha$  at each interim analysis in such a way that at the end of the study, the total Type I error does not exceed 0.025. This spending function generates boundaries that are nearly identical to the O'Brien-Fleming boundaries.

In survival trials, information time is calculated based upon number of events rather than number of subjects accrued. In practice, interim analyses are often scheduled based upon specified calendar time rather than number of events. To address the logistical inconvenience, Lan and DeMets extended their general group sequential approach for the maximum duration trial. That is, the conduct of a trial is expected to occur within some period of time  $[0, T_c]$ , where  $T_c$  is the maximum calendar (or duration) time for completion. The stopping boundaries can be adjusted based on the actual number of events observed at the interim look, rather than information fraction. This method allows flexibility in the monitoring process for accommodating any changes in terms of timing and spacing of the looks or additional examination of the data that is not pre-determined in response to the concerns from the DSMC that may arise during the course of the trial.

The analytic approach that will be used for the interim analyses for assessing treatment differences will be the time-to-event analysis method. The standardized logrank score statistic will be compared with the stopping boundaries at each interim look to draw statistical inference. If the stopping boundary is crossed, then the study will stop for effectiveness.

Judgment concerning the continuation or termination of the study will involve not only the degree of statistical significance observed at the interim analysis, but also the likelihood of achieving significance should enrollment continue to the originally projected sample size. As an aid in this latter assessment, the group sequential analyses outlined above will be supplemented with calculations of conditional power. After approximately 25% of the total number of events have occurred (1st interim look), conditional power (CP) for the primary treatment comparison will be computed and provided to the DSMC as a regular part of the interim study reports. If the CP is less than 0.2, then the study will be stopped for futility.

For example, the anticipated start time for this study is December, 2012 and the expected end of subject enrollment in June, 2014. With 3 years follow-up time, the study is expected to be completed in June, 2017. Interim looks are planned for December 2013, June 2014, December 2014, June 2015, December 2015, June 2016, and December 2016, with a final look in June 2017. The stopping boundaries for effectiveness for these scheduled looks are displayed in Table 6. If the study start time or calendar time for interim looks changes, the operating characteristics will be recalculated based upon actual calendar time of the interim looks and the number of events observed at each look.

**Table 6. Operating Characteristics for Group Sequential Design\***

Look #	Calendar Time	Information Fraction	Number of Events	Bounds	Incremental Alpha	Cumulative Alpha
1	Dec. 2013	0.22	5	4.6374	0.00000	0.00000
2	June 2014	0.33	9	3.7332	0.00009	0.00010
3	Dec. 2014	0.44	11	3.1913	0.00063	0.00073
4	June 2015	0.56	15	2.8277	0.00192	0.00265
5	Dec. 2015	0.67	20	2.5881	0.00341	0.00606
6	June 2016	0.78	22	2.3477	0.00499	0.01105
7	Dec. 2016	0.89	26	2.2183	0.00639	0.01744
8	June 2017	1	28	2.0507	0.00756	0.02500

\* Note: Time-interval related statistical deliverables are subject to change depending on the evolution of the study (e.g. delay in start-up, enrolment delay, ...).

### 13.10 Handling of Missing Data

The primary effectiveness endpoint (time to disease progression) will be conducted in the ITT population. Subjects with missing data will be included in this primary analysis. The following analyses will be used to test the robustness of the analyses results with regards to missing data:

- 1) Missing data will be censored at their last observation.
- 2) Missing data will be imputed using multiple imputation. This approach will enable an analysis to be conducted based on the full ITT population. The details of this approach will be provided in the statistical analysis plan.

### 13.11 Secondary Statistical Analyses of Primary Effectiveness Endpoint

#### 13.11.1 Per-Protocol Analysis

This analysis will be performed in the PP subject population. Propensity score weighting methodology will be applied to adjust for the imbalance of subjects' characteristics between these two groups. Cross-over subjects will be added to the ablation group and the time-dependent covariate will be used to account for the different timing of cross-over. A propensity score weighted Cox proportional hazards model will be used to compare the hazard rate between the two groups at observed death times. Diagnosis analyses will be performed to examine the assumption of proportional hazards. If the proportional hazards assumption is not met, then the interaction effect of time by treatment group and other remedy analyses will be investigated. The adjusted hazard ratio and its 95% confidence intervals will be reported for the two groups. Missing primary effectiveness endpoint data and the associated covariates that will be included in the propensity score modeling will be imputed using the multiple imputation method.

#### 13.11.2 Subgroup Analyses

The primary effectiveness analysis (KM analysis of time to persistent AF/AT) will be performed for the Test Group as randomized and for the Control Group as randomized (excluding cross-over subjects). The cross-over subjects (i.e., continued on their current

AAD or taking a newly prescribed AAD and had an RF ablation procedure) will be analyzed separately as a third group.

- Test Group: randomized to RF ablation to achieve PVI using the CARTO® 3, CARTO® XP or CARTO® RMT System, and THERMOCOOL® Catheter Family
- Control Group: randomized to AAD therapy in accordance with current AF management guidelines
- Cross-over Group: Control Group subjects who undergo RF ablation to achieve PVI using the CARTO® 3, CARTO® XP or CARTO® System, and THERMOCOOL® Catheter Family

The median time to persistent AF/AT as well as the 95% confidence intervals will be reported for the three groups. The survival probability and rate of persistent AF/AT at 3 years follow-up as well as the 95% confidence intervals for these three groups will be presented separately.

### **13.12 Secondary Effectiveness Endpoints Analyses**

#### **13.12.1 Rate and Time to Persistent AF/AT at 1 year, 2 and 3 years follow-up by number of ablations**

For the secondary effectiveness endpoint, the rate and time to persistent AF/AT (excluding isthmus dependent atrial flutter) at 1 year and 2 years and the rate of persistent AF/AT at 3 years by number of ablations, a KM analysis will be performed to examine the hazard function of persistent AF/AT (excluding isthmus dependent atrial flutter) for the two treatment groups at 1 year follow-up time and 2 year follow-up and 3 year follow-up in the Test Group by the number of ablations. Data will be censored at 1 year and 2 year follow-up in two separate analyses. The analysis will be performed in both the ITT and PP populations. A log-rank test will be used to compare the hazard functions between the two groups at any observed event time. The median time to persistent AF/AT at 1 year and 2 year follow-up as well as the 95% confidence intervals will be reported by the two groups. The survival probability and rate of persistent AF/AT at 1 year and 2 years follow-up as well as the 95% confidence intervals for the two groups will be presented.

The median time to persistent AF/AT at 3 years follow-up as well as the 95% confidence intervals will be reported for the Test Group by the number of ablations. The survival probability and rate of persistent AF/AT at 3 years follow-up as well as the 95% confidence intervals for the Test Group will also be presented by the number of ablations. The KM curves will be plotted and results will be listed as well.

#### **13.12.2 Number of Repeat Ablations and New AAD Drugs**

To analyze this secondary effectiveness endpoint, number of repeat ablations and new AAD drugs per subject throughout 3 years follow-up and the number of repeat ablations will be summarized and listed for the subjects who have undergone at least one ablation. In addition, new AAD use will be summarized and listed for the subjects in the two groups by drug category and specific drug. The analyses will be performed in both ITT and PP populations.

#### **13.12.3 Rhythm Throughout 3 Years Follow-up**

To analyze this secondary effectiveness endpoint, rhythm (% subjects in sinus rhythm, % subjects with recurrent AF) throughout 3 years follow-up, the number of subjects and percentage of subjects with sinus rhythm and the number of subjects and percentage of subjects with recurrent AF/AT during the 3 year follow-up time will be summarized and listed by the two groups. The analyses will be performed in both ITT and PP populations.

#### **13.12.4 Factors Associated with AF Disease Progression**

To analyze this secondary endpoint, conditions that may be associated with disease progression will be assessed at baseline and throughout the 3-year follow-up period. These targeted parameters include: LA size at baseline and subsequent increase above baseline size; age  $\geq 60$  years; HATCH score at baseline and subsequent increase above baseline score; hypertension; NYHA Functional Classification of heart disease; diabetes; hyperlipidemia/dyslipidemia; renal insufficiency; and, dementia. A Cox proportional hazards model will be performed to examine the associations of time with disease progression. To document pre-existing diseases, measurable baseline parameters will include age, gender, LA size, AF duration, NYHA Functional Classification of heart disease, HATCH score, blood pressure, lipid profile, renal function and the presence of diabetes and/or dementia. The Cox proportional hazards model will also be used to examine time-varying covariates, based upon each follow-up visit and either as a new onset disorder or a worsened diagnosis since a previous assessment. These analyses will include all follow-up assessments throughout the 3-year study period and measurable parameters will include: LA size; HATCH Score; blood pressure; NYHA Functional Classification of heart disease; diabetes; lipid profile; renal function and, dementia. All analyses will control for treatment assignment. Any significant interactions between treatment effect(s) and covariates will also be examined.

Univariate analysis will be performed to screen for significant factors associated with disease progression at p-value  $<0.2$ . Then multivariate analyses will be performed to identify any factors associated with disease progression at p-value  $<0.05$ . Model selection methods (e.g., Akaike Information Criteria [AIC], stepwise) will be applied to identify the best set of factors linked to disease progression. The identification of relevant associations provides additional characterization and interpretation of the primary effectiveness outcome. These analyses will be performed in both the ITT and PP populations.

Descriptive statistics will be used to summarize the baseline and follow-up values of LA size, HATCH score, blood pressure, NYHA Functional Classification of heart disease, diabetes, lipid profile, renal function, and dementia by treatment groups. Change-from-baseline will also be summarized and listed. Paired-sample test will be used to test whether the change from baseline values differs from zero (e.g., paired t-test, McNeman's test) within each treatment group. A two-sample comparison of the two groups with respect to changes in these characteristics will be performed using general linear models, including the baseline value as a covariate and assessing treatment group differences.

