### 13.4 Sample Size and Power Calculation

A total sample size of 322 (161:161) subjects will be required to ensure 85% power to detect the effect size measured by negative log of the hazard ratio equal to 1.154f (treatment group over control group). This calculation assumes a 50% cross-over rate from the AAD group to the ablation group, a 10% drop-out rate in each group over the 3 year follow-up period, and 1.5 years accrual time. This calculation is based upon one-sided superiority testing with alpha equal to 0.025. Using meta-analysis, the rates of disease progression at the end of follow-up are estimated to be 25% and 5% in the AAD and ablation group, respectively (see the point estimate justification document for details, Appendix C). The sample size calculation is based upon the method developed by Rubinstein, Gail and Santner (RGS,1981) and also incorporates group sequential design with multiple interim looks.

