6. SAMPLE SIZE DETERMINATION

A total sample size of 322 (161:161) subjects will be required to ensure 85% power to detect the effect size measured by negative log of the hazard ratio equal to 1.1541 (treatment group over control group).

$$-\log_e \left(\frac{\hat{\lambda}_t}{\hat{\lambda}_c} \right) = -\log_e \left(\left(-\frac{\log_e(0.95)}{3} \right) / \left(-\frac{\log_e(0.85)}{3} \right) \right) = 1.1541$$

This calculation assumes a 50% cross-over rate from the AAD group to the ablation group, a 10% drop-out rate in each group over the 3 year follow-up period, and 1.5 years accrual time. This calculation is based upon one-sided superiority testing with alpha equal to 0.025. Using meta-analysis, the rates of disease progression at the end of follow-up are estimated to be 25% and 5% in the AAD and ablation group, respectively (see the point estimate justification document for details, Appendix C of the CTP). The cross-over to ablation is reflected in the use of the proportion 0.85 instead of 0.75 in the formula above. The sample size calculation is based upon the method developed by Rubinstein, Gail and Santner⁴ (RGS, 1981) and also incorporates group sequential design with multiple interim looks.

Adaptive Sample Size Re-estimation

Due to the uncertainties associated with the cross-over rate and the effect size, the sample size will be reestimated at the time of the first interim analysis. Conditional power (CP) will be calculated at that time to determine how promising the interim results are. CP is defined as the conditional probability that the final result will exceed a critical value given the data observed thus far, and the assumption that the trend to be observed in the remainder of the study⁵ will follow the expectation, which was used in the original sample size calculation. If the CP is less than 0.3, then the study is considered not promising, and the sample size will not be increased. If the CP is

greater than 0.9, then the study is deemed fully powered and the sample size will not be increased. If the CP falls in the promising zone (0.3-0.9), the sample size will be re-estimated based upon the observed effect size.

In detail, the following formula will be applied to re-estimate the sample size:

$$M = N \left(\frac{\delta}{\Delta} \right)^2$$

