10.6.4 Factors Associated with AF Disease Progression

To analyze this secondary endpoint, conditions that may be associated with disease progression will be assessed at baseline and throughout the 3-year follow-up period.

Cox proportional hazards models will be used to examine the associations of baseline-variables with time to disease progression. Time to disease progression is referring to time to persistent AF/AT (primary endpoint) in this section. The following baseline variables will be investigated:

- gender
- age (categories: <75 years, ≥75 years)
- LA size (Parasternal long axis view from transthoracic echocardiogram) (not large: ≤ 55mm/large: >55mm)
- AF duration (continuous)
- number of AF events in 6 months prior to trial
- heart failure (yes vs. no) (as specified in HATCH score component)
- hypertension (yes [past or present] vs. no)
- hyperlipidemia/dyslipidemia (yes [past or present] vs. no)
- renal insufficiency (yes [past or present] vs. no)
- diabetes (yes vs. no)
- dementia (yes vs. no)
- previous TIA or stroke (yes vs. no) (as specified in HATCH score component)
- previous COPD (yes vs. no)(as specified in HATCH score component)

For the baseline variables, in a first step, single covariate Cox models including the

respective covariate, the treatment factor and the covariate*treatment interaction term will be fitted. In a second step, a multivariate Cox model will be fitted including the treatment factor and all covariates plus covariate*treatment interaction terms for which either the covariate or the interaction term had been associated with time to disease progression with a p-value < 0.2 in the single variate model. The Stepwise option of PROC PHREG will be used for model selection, setting the level for covariates to enter and to stay in the model to 0.05.

These analyses will be performed in the ITT and PP populations (with fixed treatment effect in the PP population).

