Moreover, in the PP population the following analysis will be performed modelling the treatment effect as time-dependent covariate and additionally including baseline covariates: in a first step, single covariate Cox models including the respective covariate and the treatment factor (as time-dependent covariate) will be fitted. In a second step, a multivariate Cox model will be fitted including the treatment factor (as time-dependent covariate) and all covariates which had been associated with time to disease progression with a p-value < 0.2 in the single variate model. The Stepwise option of PROC PHREG will be used for model selection, setting the level for covariates to enter and to stay in the model to 0.05.

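### The progression-factor analysis in SAP 10.6.4 selects covariates and treatment interactions stepwise on about 28 to 31 planned events; it would name a chance factor in roughly 35-49% of trials and overstate the factors it keeps (minor)

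*Protocol*

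**What the plan says.** Protocol 13.12.4 sets out a general two-step approach. First, "Univariate analysis will be performed to screen for significant factors associated with disease progression" at p<0.2. Then come multivariate models at p<0.05, for which "Model selection methods (e.g., Akaike Information Criteria [AIC], stepwise) will be applied to identify the best set of factors linked to disease progression". It asks for significant treatment-by-covariate interactions to be examined, but does not put interactions through the screen.

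SAP 10.6.4 supplies the working rule:

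- It lists 13 baseline covariates: gender, age group, LA size (above 55 mm or not), AF duration, number of recent AF events, heart failure, hypertension, hyperlipidemia, renal insufficiency, diabetes, dementia, previous TIA or stroke, and COPD.
- Each is first fitted alone with treatment and its treatment interaction.
- In the second step "a multivariate Cox model will be fitted including the treatment factor and all covariates plus covariate*treatment interaction terms", for every covariate where either term had p<0.2. PHREG stepwise selection follows, at 0.05 to enter and to stay.
- This is done in ITT and in PP with fixed treatment. A further PP run has time-dependent treatment and no interactions, and carries forward "all covariates which had been associated with time to disease progression with a p-value < 0.2 in the single variate model".

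SAP 5.1 removes some supporting models for this endpoint but keeps this procedure. Neither document gives it multiplicity control, shrinkage, internal validation, a cap on candidate terms or an exploratory label.

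**The concern.** Stepwise selection after a screen reports ordinary Cox p-values and hazard ratios, as if the retained factors had been chosen in advance. With very few events per candidate term, two things follow. Chance associations are retained far more often than 5% of the time. And a retained factor must show a large estimate to be retained at all, so its hazard ratio is biased away from 1.

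The endpoint is a named secondary one, and Protocol 13.12.4 intends it to help interpret the primary result. At stake is a report that names risk factors for progression, or modifiers of the ablation effect, that would not replicate. No success criterion depends on it.

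**Working it through.** **Inputs**

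- Sample size: "A total sample size of 322 (161:161) subjects will be required to ensure 85% power" (Protocol 13.4).
- Primary test, used here only to check the event count: "one-sided superiority testing with alpha equal to 0.025" (Protocol 13.4).
- Three-year progression: 5% Test; 25% Control, diluted to 15%. SAP 6: "The cross-over to ablation is reflected in the use of the proportion 0.85 instead of 0.75 in the formula above".
- Drop-out: 10% per arm over 3 years (Protocol 13.4).
- Final look, Protocol Table 6: "8 June 2017 1 28 2.0507 0.00756 0.02500", that is 28 events.

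**1. The planned events reproduce.** The hazard ratio is ln(0.95)/ln(0.85) = 0.3156, and its negative log is 1.153. Schoenfeld's formula gives 4 × (1.960 + 1.036)² / 1.153² = 27.004, which rounds up to the stated 28. From the rates, 161 × 0.05 = 8.05 Test and 161 × 0.15 = 24.15 Control, or 32.2 before drop-out. With 10% drop-out and 3 years of follow-up, simulation gives 30.6 (7.6 in Test).

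**2. Events per candidate term.** Two of the 13 covariates should hardly vary. LA diameter above 55 mm is barred by inclusion criterion 5 (Protocol 9.3), and the dementia footnote to Protocol 10.2 says that baseline dementia precludes enrolment. Eleven covariates with 11 interactions make 22 terms: 28/22 = 1.3 and 31/22 = 1.4 events per term.

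**3. False selection when no factor matters.** As a benchmark, 11 independent tests at 0.05 give 1 − 0.95^11 = 43%. The SAP rule was then simulated for one ITT run: 322 subjects, rates 5%/15%, 10% drop-out, treatment kept in, Wald p<0.2 on covariate or interaction, then score entry and Wald stay at 0.05. The 11 covariates were 9 binary and 2 continuous, generated independently, with 5,000 replicates per setting. The SAP does not say whether an interaction may enter without its main effect, so both cases are shown.

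| Binary prevalences (assumed) | Interaction only after main effect | No such hierarchy |
|---|---|---|
| Mixed, 10-80% | 34.5% | 48.9% |
| All 40% | 38.4% | 47.3% |

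With mixed prevalences and about 24 events the figures are 32.7% and 45.6%; with about 37 events, 35.5% and 50.8%. Counting a false factor in any of the three planned runs (PP populations approximated, 3,000 replicates) gives 44% and 62%.

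**4. Overstatement.** At 28 events a binary factor of prevalence p reaches two-sided p<0.05 only if its estimated hazard ratio is about exp(1.96/√(28p(1−p))) or its inverse. That is 2.1 at p = 0.5 and 3.4 at p = 0.1. Simulated selection (main effects only, 13 covariates, prevalence 40%, about 30 events) gives these geometric mean hazard ratios when the factor is kept:

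| True HR | How often kept | Reported HR when kept |
|---|---|---|
| 1.25 | 9% | 2.24 |
| 1.5 | 20% | 2.51 |
| 2.0 | 47% | 2.80 |
| 3.0 | 83% | 3.50 |

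**5. Estimability of the interactions.** With 8 Test events, the chance that none falls in the exposed category is 0.9^8 = 0.43 at 10% prevalence and 0.8^8 = 0.17 at 20%. Take the mixed set (42, 20, 12, 80, 40, 10, 15, 10 and 10%). The chance that one category is empty of Test events is (1−p)^8 + p^8 for each factor. These sum to 2.3 of the 9 factors, and the chance that at least one factor is affected is 94%. Such an interaction has an infinite estimate and a Wald p near 1, so the screen says nothing about it.

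**The case against.** The case on the other side has several parts.

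- **The rate.** A reader might infer that the procedure names a false factor about half the time. With 11 usable covariates that holds only if interactions may enter without their main effects; with a hierarchy it is 35-38%. Correlation among covariates would lower the rate somewhat. This stands, and a range is the right statement.
- **Thirteen covariates and 26 terms.** A reader might count one event per term. Two covariates barely vary by eligibility, so about 22 terms is fair.
- **The Protocol.** A reader might attribute the 13-covariate interaction screen to Protocol 13.12.4. It is in SAP 10.6.4 only.
- **Empty cells.** A reader might infer that inestimable interactions create false effect modifiers. A Wald p near 1 keeps that interaction from passing the screen itself. The defect is that the screen is uninformative for these terms.
- **Only survivors are reported.** They are not: planned Table 14.2.10.1 shows the single-covariate models in ITT and PP, and Table 14.2.10.3 shows those with time-dependent treatment.
- **Stakes.** The endpoint carries no alpha. Protocol 5.1 cites prior evidence for age and HATCH components, so a null in which nothing matters is a worst case. This stands and limits the severity.

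What remains is the selection step. Even the lower end, about 35%, is seven times 5%. The inflation of kept hazard ratios does not need the null; it occurs when the factors are real.

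**Conclusion.** The point holds at minor severity. As written, SAP 10.6.4 would name at least one factor in about 35-49% of trials when none matters, for one ITT run with 11 usable covariates. A true hazard ratio of 1.5 would be reported at about 2.5 when kept. Treatment interactions will often rest on no Test event in one category.

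The percentages rest on assumed prevalences, independent covariates, and Wald screening with score-test entry; the documents give neither the prevalences nor the hierarchy setting. The event count is a planning figure. SAP 5.1 says that the trial stopped early, and the final number is not given, but the result changes little between about 24 and 37 events.

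A reader might infer that the trial's main conclusion is compromised. It is not: the ITT log-rank test uses none of this.

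**What to change.** In SAP 10.6.4:

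1. Drop the p<0.2 screen and the stepwise step from all three runs.
2. Remove the LA split at 55 mm and use LA size as a continuous variable. Remove baseline dementia.
3. Fit one main-effects Cox model with treatment forced in and three or four factors named before database lock, using Firth estimation. At 28 events this is 28/5 = 5.6 to 28/4 = 7 events per parameter.
4. Do not select interactions.
5. Keep the single-covariate display (Table 14.2.10.1) for the remaining covariates, as hazard ratios with 95% confidence intervals, reported whatever their p-values.
6. Label the results exploratory. The label is still needed: three or four independent factors each read at 0.05 have a 14% to 19% chance of at least one false positive (1 − 0.95³ and 1 − 0.95⁴).

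The cost is SAP wording and somewhat less programming. The downside is that fewer covariates are adjusted for one another.
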